	Grade 2	
Hold study drug/study regimen dose until resolution to Grade \leq1.
 
Permanently discontinue study drug/study regimen if it does not resolve to Grade \leq1 within 30 days or if there are signs of respiratory insufficiency or autonomic instability.
	
For Grade 2:
 
 - Consider, as necessary, discussing with the study physician. - Care should be taken to monitor patients for sentinel symptoms of a potential decompensation as described above. - Obtain a neurology consult - Sensory neuropathy/neuropathic pain may be managed by appropriate medications (e.g., gabapentin or duloxetine). 
MYASTHENIA GRAVIS:
 
 o Steroids may be successfully used to treat myasthenia gravis. It is important to consider that steroid therapy (especially with high doses) may result in transient worsening of myasthenia and should typically be administered in a monitored setting under supervision of a consulting neurologist. o Patients unable to tolerate steroids may be candidates for treatment with plasmapheresis or IV IG. Such decisions are best made in consultation with a neurologist, taking into account the unique needs of each patient. o If myasthenia gravis-like neurotoxicity is present, consider starting AChE inhibitor therapy in addition to steroids. Such therapy, if successful, can also serve to reinforce the diagnosis. 
GUILLAIN-BARRE:
 
 o It is important to consider here that the use of steroids as the primary treatment of Guillain-Barre is not typically considered effective. o Patients requiring treatment should be started with IV IG and followed by plasmapheresis if not responsive to IV IG.

Specific Immune-Mediated Reactions			
Adverse Events	Severity Grade of the Event (NCI CTCAE version 4.03)	Dose Modifications	Toxicity Management
	Grade 3 or 4	
For Grade 3: Hold study drug/study regimen dose until resolution to Grade \leq1. Permanently discontinue study drug/study regimen if Grade 3 imAE does not resolve to Grade \leq1 within 30 days or if there are signs of respiratory insufficiency or autonomic instability.
 
For Grade 4: Permanently discontinue study drug/study regimen.
	
For Grade 3 or 4 (severe or life-threatening events):
 
 - Consider, as necessary, discussing with study physician. - Recommend hospitalization. - Monitor symptoms and obtain neurological consult. 
MYASTHENIA GRAVIS:
 
 o Steroids may be successfully used to treat myasthenia gravis. They should typically be administered in a monitored setting under supervision of a consulting neurologist. o Patients unable to tolerate steroids may be candidates for treatment with plasmapheresis or IV IG. o If myasthenia gravis-like neurotoxicity present, consider starting AChE inhibitor therapy in addition to steroids. Such therapy, if successful, can also serve to reinforce the diagnosis. 
GUILLAIN-BARRE:
 
 o It is important to consider here that the use of steroids as the primary treatment of Guillain-Barre is not typically considered effective. o Patients requiring treatment should be started with IV IG and followed by plasmapheresis if not responsive to IV IG.

Specific Immune-Mediated Reactions			
Adverse Events	Severity Grade of the Event (NCI CTCAE version 4.03)	Dose Modifications	Toxicity Management
Myocarditis	Any Grade	
General Guidance Discontinue drug permanently if biopsy-proven immune-mediated myocarditis.
	
For Any Grade:
 
 – The prompt diagnosis of immune-mediated myocarditis is important, particularly in patients with baseline cardiopulmonary disease and reduced cardiac function. – Consider, as necessary, discussing with the study physician. – Monitor patients for signs and symptoms of myocarditis (new onset or worsening chest pain, arrhythmia, shortness of breath, peripheral edema). As some symptoms can overlap with lung toxicities, simultaneously evaluate for and rule out pulmonary toxicity as well as other causes (e.g., pulmonary embolism, congestive heart failure, malignant pericardial effusion). A Cardiology consultation should be obtained early, with prompt assessment of whether and when to complete a cardiac biopsy, including any other diagnostic procedures. – Initial work-up should include clinical evaluation, BNP, cardiac enzymes, ECG, echocardiogram (ECHO), monitoring of oxygenation via pulse oximetry (resting and exertion), and additional laboratory work-up as indicated. Spiral CT or cardiac MRI can complement ECHO to assess wall motion abnormalities when needed. – Patients should be thoroughly evaluated to rule out any alternative etiology (e.g., disease progression, other medications, or infections)

Specific Immune-Mediated Reactions			
Adverse Events	Severity Grade of the Event (NCI CTCAE version 4.03)	Dose Modifications	Toxicity Management
	Grade 1 (asymptomatic with laboratory (e.g., BNP) or cardiac imaging abnormalities)	No dose modifications required unless clinical suspicion is high, in which case hold study drug/study regimen dose during diagnostic work-up for other etiologies. If study drug/study regimen is held, resume after complete resolution to Grade 0.	For Grade 1 (no definitive findings): 
 – Monitor and closely follow up in 2 to 4 days for clinical symptoms, BNP, cardiac enzymes, ECG, ECHO, pulse oximetry (resting and exertion), and laboratory work-up as clinically indicated. – Consider using steroids if clinical suspicion is high.
	Grade 2, 3 or 4 (Grade 2: Symptoms with mild to moderate activity or exertion) (Grade 3: Severe with symptoms at rest or with minimal activity or exertion; intervention indicated) (Grade 4: Life-threatening consequences; urgent intervention indicated (e.g., continuous IV therapy or mechanical hemodynamic support))	If Grade 2 -- Hold study drug/study regimen dose until resolution to Grade 0. If toxicity rapidly improves to Grade 0, then the decision to reinstitute study drug/study regimen will be based upon treating physician's clinical judgment and after completion of steroid taper. If toxicity does not rapidly improve, permanently discontinue study drug/study regimen. If Grade 3-4, permanently discontinue study drug/study regimen.	For Grade 2-4: 
 – Monitor symptoms daily, hospitalize. – Promptly start IV methylprednisolone 2 to 4 mg/kg/day or equivalent after Cardiology consultation has determined whether and when to complete diagnostic procedures including a cardiac biopsy. – Supportive care (e.g., oxygen). – If no improvement within 3 to 5 days despite IV methylprednisolone at 2 to 4 mg/kg/day, promptly start immunosuppressive therapy such as TNF inhibitors (e.g., infliximab at 5 mg/kg every 2 weeks). Caution: It is important to rule out sepsis and refer to infliximab label for general guidance before using infliximab. – Once the patient is improving, gradually taper steroids over ≥28 days and consider prophylactic antibiotics, antifungals, or anti-PJP treatment (refer to current NCCN guidelines for treatment of cancer-related infections [Category 2B recommendation]).^a
Myositis/Polymyositis (“Poly/myositis”)	Any Grade	General Guidance	For Any Grade: 
 – Monitor patients for signs and symptoms of poly/myositis. Typically, muscle weakness/pain occurs in proximal muscles including upper arms, thighs, shoulders, hips, neck and back,

Specific Immune-Mediated Reactions			
Adverse Events	Severity Grade of the Event (NCI CTCAE version 4.03)	Dose Modifications	Toxicity Management
			
but rarely affects the extremities including hands and fingers; also difficulty breathing and/or trouble swallowing can occur and progress rapidly. Increased general feelings of tiredness and fatigue may occur, and there can be new-onset falling, difficulty getting up from a fall, and trouble climbing stairs, standing up from a seated position, and/or reaching up.
 
 – If poly/myositis is suspected, a Neurology consultation should be obtained early, with prompt guidance on diagnostic procedures. Myocarditis may co-occur with poly/myositis; refer to guidance under Myocarditis. Given breathing complications, refer to guidance under Pneumonitis/ILD. Given possibility of an existent (but previously unknown) autoimmune disorder, consider Rheumatology consultation. – Consider, as necessary, discussing with the study physician. – Initial work-up should include clinical evaluation, creatine kinase, aldolase, LDH, BUN/creatinine, erythrocyte sedimentation rate or C-reactive protein level, urine myoglobin, and additional laboratory work-up as indicated, including a number of possible rheumatological/antibody tests (i.e., consider whether a rheumatologist consultation is indicated and could guide need for rheumatoid factor, antinuclear antibody, anti-smooth muscle, antisynthetase [such as anti-Jo-1], and/or signal-recognition particle antibodies). Confirmatory testing may include electromyography, nerve conduction studies, MRI of the muscles, and/or a muscle biopsy. Consider Barium swallow for evaluation of dysphagia or dysphonia. – Patients should be thoroughly evaluated to rule out any alternative etiology (e.g., disease progression, other medications, or infections).

Specific Immune-Mediated Reactions			
Adverse Events	Severity Grade of the Event (NCI CTCAE version 4.03)	Dose Modifications	Toxicity Management
	Grade 1 (mild pain)	No dose modifications.	For Grade 1: 
 - Monitor and closely follow up in 2 to 4 days for clinical symptoms and initiate evaluation as clinically indicated. - Consider Neurology consult. - Consider, as necessary, discussing with the study physician.
	Grade 2 (moderate pain associated with weakness; pain limiting instrumental activities of daily living [ADLs])	Hold study drug/study regimen dose until resolution to Grade ≤ 1 . Permanently discontinue study drug/study regimen if it does not resolve to Grade ≤ 1 within 30 days or if there are signs of respiratory insufficiency.	For Grade 2: 
 - Monitor symptoms daily and consider hospitalization. - Obtain Neurology consult, and initiate evaluation. - Consider, as necessary, discussing with the study physician. - If clinical course is rapidly progressive (particularly if difficulty breathing and/or trouble swallowing), promptly start IV methylprednisolone 2 to 4 mg/kg/day systemic steroids along with receiving input from Neurology consultant - If clinical course is not rapidly progressive, start systemic steroids (e.g., prednisone 1 to 2 mg/kg/day PO or IV equivalent); if no improvement within 3 to 5 days, continue additional work up and start treatment with IV methylprednisolone 2 to 4 mg/kg/day - If after start of IV methylprednisolone at 2 to 4 mg/kg/day there is no improvement within 3 to 5 days, consider start of immunosuppressive therapy such as TNF inhibitors (e.g., infliximab at 5 mg/kg every 2 weeks). Caution: It is important to rule out sepsis and refer to infliximab label for general guidance before using infliximab. - Once the patient is improving, gradually taper steroids over ≥ 28 days and consider prophylactic antibiotics, antifungals, or anti-PJP treatment (refer to current NCCN guidelines for treatment of cancer-related infections [Category 2B recommendation]).^a

Specific Immune-Mediated Reactions			
Adverse Events	Severity Grade of the Event (NCI CTCAE version 4.03)	Dose Modifications	Toxicity Management
	Grade 3 or 4 (pain associated with severe weakness; limiting self-care ADLs)	
For Grade 3: Hold study drug/study regimen dose until resolution to Grade \leq1. Permanently discontinue study drug/study regimen if Grade 3 imAE does not resolve to Grade \leq1 within 30 days or if there are signs of respiratory insufficiency.
 
For Grade 4: Permanently discontinue study drug/study regimen.
	
For Grade 3 or 4 (severe or life-threatening events):
 
 - Monitor symptoms closely; recommend hospitalization. - Obtain Neurology consult, and complete full evaluation. - Consider, as necessary, discussing with the study physician. - Promptly start IV methylprednisolone 2 to 4 mg/kg/day systemic steroids along with receiving input from Neurology consultant. - If after start of IV methylprednisolone at 2 to 4 mg/kg/day there is no improvement within 3 to 5 days, consider start of immunosuppressive therapy such as TNF inhibitors (e.g., infliximab at 5 mg/kg every 2 weeks). Caution: It is important to rule out sepsis and refer to infliximab label for general guidance before using infliximab. - Consider whether patient may require IV IG, plasmapheresis. - Once the patient is improving, gradually taper steroids over \geq28 days and consider prophylactic antibiotics, antifungals, or anti-PJP treatment (refer to current NCCN guidelines for treatment of cancer-related infections [Category 2B recommendation]).^a

^a ASCO Educational Book 2015 “Managing Immune Checkpoint Blocking Antibody Side Effects” by Michael Postow MD.

^b FDA Liver Guidance Document 2009 Guidance for Industry: Drug Induced Liver Injury – Premarketing Clinical Evaluation.

AChE Acetylcholine esterase; ADL Activities of daily living; AE Adverse event; ALP Alkaline phosphatase test; ALT Alanine aminotransferase; AST Aspartate aminotransferase; BUN Blood urea nitrogen; CT Computed tomography; CTCAE Common Terminology Criteria for Adverse Events; ILD Interstitial lung disease; imAE immune-mediated adverse event; IG Immunoglobulin; IV Intravenous; GI Gastrointestinal; LFT Liver function tests; LLN Lower limit of normal; MRI Magnetic resonance imaging; NCI National Cancer Institute; NCCN National Comprehensive Cancer Network; PJP *Pneumocystis jirovecii* pneumonia (formerly known as *Pneumocystis carinii* pneumonia); PO By mouth; T3 Triiodothyronine; T4 Thyroxine; TB Total bilirubin; TNF Tumor necrosis factor; TSH Thyroid-stimulating hormone; ULN Upper limit of normal.

Infusion-Related Reactions		
Severity Grade of the Event (NCI CTCAE version 4.03)	Dose Modifications	Toxicity Management
Any Grade	General Guidance	For Any Grade: 
 - Manage per institutional standard at the discretion of investigator. - Monitor patients for signs and symptoms of infusion-related reactions (e.g., fever and/or shaking chills, flushing and/or itching, alterations in heart rate and blood pressure, dyspnea or chest discomfort, or skin rashes) and anaphylaxis (e.g., generalized urticaria, angioedema, wheezing, hypotension, or tachycardia).
Grade 1 or 2	For Grade 1: The infusion rate of study drug/study regimen may be decreased by 50% or temporarily interrupted until resolution of the event. For Grade 2: The infusion rate of study drug/study regimen may be decreased 50% or temporarily interrupted until resolution of the event. Subsequent infusions may be given at 50% of the initial infusion rate.	For Grade 1 or 2: 
 - Acetaminophen and/or antihistamines may be administered per institutional standard at the discretion of the investigator. - Consider premedication per institutional standard prior to subsequent doses. - Steroids should not be used for routine premedication of Grade ≤ 2 infusion reactions.
Grade 3 or 4	For Grade 3 or 4: Permanently discontinue study drug/study regimen.	For Grade 3 or 4: 
 - Manage severe infusion-related reactions per institutional standards (e.g., IM epinephrine, followed by IV diphenhydramine and ranitidine, and IV glucocorticoid).

CTCAE Common Terminology Criteria for Adverse Events; IM intramuscular; IV intravenous; NCI National Cancer Institute.

Non-Immune-Mediated Reactions		
Severity Grade of the Event (NCI CTCAE version 4.03)	Dose Modifications	Toxicity Management
Any Grade	Note: Dose modifications are not required for AEs not deemed to be related to study treatment (i.e., events due to underlying disease) or for laboratory abnormalities not deemed to be clinically significant.	Treat accordingly, as per institutional standard.
Grade 1	No dose modifications.	Treat accordingly, as per institutional standard.
Grade 2	Hold study drug/study regimen until resolution to \leq Grade 1 or baseline.	Treat accordingly, as per institutional standard.
Grade 3	Hold study drug/study regimen until resolution to \leq Grade 1 or baseline. For AEs that downgrade to \leq Grade 2 within 7 days or resolve to \leq Grade 1 or baseline within 14 days, resume study drug/study regimen administration. Otherwise, discontinue study drug/study regimen.	Treat accordingly, as per institutional standard.
Grade 4	Discontinue study drug/study regimen (Note: For Grade 4 labs, decision to discontinue should be based on accompanying clinical signs/symptoms, the Investigator's clinical judgment, and consultation with the Sponsor.).	Treat accordingly, as per institutional standard.

AE Adverse event; CTCAE Common Terminology Criteria for Adverse Events; NCI National Cancer Institute.

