- $AST \geq 3 \times ULN$
- $total\ bilirubin \geq 2 \times ULN$

The Investigator will without delay review each new laboratory report and if the identification criteria are met will:

- Notify the AstraZeneca representative
- Determine whether the subject meets PHL criteria (see Appendix D 2 for definition) by reviewing laboratory reports from all previous visits
- Promptly enter the laboratory data into the laboratory CRF

D 4 Follow-up

D 4.1 Potential Hy's Law criteria not met

If the subject does not meet PHL criteria the Investigator will:

- Perform follow-up on subsequent laboratory results according to the guidance provided in the Clinical Study Protocol.

D 4.2 Potential Hy's Law criteria met

If the subject does meet PHL criteria the Investigator will:

- Notify the AstraZeneca representative who will then inform the central Study Team
The Study Physician contacts the Investigator, to provide guidance, discuss and agree an approach for the study subjects' follow-up and the continuous review of data. Subsequent to this contact the Investigator will:
- Monitor the subject until liver biochemistry parameters and appropriate clinical symptoms and signs return to normal or baseline levels, or as long as medically indicated
- Investigate the aetiology of the event and perform diagnostic investigations as discussed with the Study Physician.
- Complete the three Liver CRF Modules as information becomes available
- If at any time (in consultation with the Study Physician) the PHL case meets serious criteria, report it as an SAE using standard reporting procedures.

D 5 Review and assessment of potential Hy's Law cases

The instructions in this section should be followed for all cases where PHL criteria are met.

No later than 3 weeks after the biochemistry abnormality was initially detected, the Study Physician contacts the Investigator in order to review available data and agree on whether there is an alternative explanation for meeting PHL criteria other than DILI caused by the investigational product. The AstraZeneca Global Clinical Lead or equivalent and Global Safety Physician will also be involved in this review together with other subject matter experts as appropriate.

According to the outcome of the review and assessment, the Investigator will follow the instructions below.

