[#]A 'significant' change in the subject's condition refers to a clinically relevant change in any of the individual liver biochemistry parameters (ALT, AST or total bilirubin) in isolation or in combination, or a clinically relevant change in associated symptoms. The determination of whether there has been a significant change will be at the discretion of the Investigator, this may be in consultation with the Study Physician if there is any uncertainty.

D 7 Actions required for repeat episodes of potential Hy's Law

This section is applicable when a subject meets PHL criteria on study treatment, and has already met PHL criteria at a previous on study treatment visit.

The requirement to conduct follow-up, review, and assessment of a repeat occurrence(s) of PHL is based on the nature of the alternative cause identified for the previous occurrence.

The investigator should determine the cause for the previous occurrence of PHL criteria being met and answer the following question:

Was the alternative cause for the previous occurrence of PHL criteria being met found to be the disease under study (e.g., chronic or progressing malignant disease, severe infection or liver disease), or did the subject meet PHL criteria prior to starting study treatment and at first on-study treatment visit, as described in Appendix D 6

If **No**: Follow the process described in Appendix D 4.1.

If **Yes**: Determine if there has been a significant[#] change in the subject's condition compared with when PHL criteria were previously met.

- If there is no significant change, no action is required.
- If there is a significant change, follow the process described in Appendix D 4.

[#]A 'significant' change in the subject's condition refers to a clinically relevant change in any of the individual liver biochemistry parameters (ALT, AST or total bilirubin) in isolation or in combination, or a clinically relevant change in associated symptoms. The determination of whether there has been a significant change will be at the discretion of the Investigator; this may be in consultation with the Study Physician if there is any uncertainty.

Appendix E Guidelines for Evaluation of Objective Tumor Response Using RECIST 1.1 (Response Evaluation Criteria in Solid Tumors)

Introduction

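### Appendix D 7 sends some repeat potential Hy's Law cases to D 4.1, the path for subjects who do not meet the criteria

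*Supplement*

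**What the plan says.** Appendix D 7 sets its own scope: "This section is applicable when a subject meets PHL criteria on study treatment", with the further condition that the criteria were already met at a previous on-treatment visit. It then makes handling conditional on the earlier episode: "The requirement to conduct follow-up, review, and assessment of a repeat occurrence(s) of PHL is based on the nature of the alternative cause" found at that time.

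The investigator answers one question: was the earlier episode explained by the disease under study, or is this the situation described in D 6? There are three outcomes:

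- No: "Follow the process described in Appendix D 4.1".
- Yes, without significant change: nothing further is required.
- Yes, with significant change: "If there is a significant change, follow the process described in Appendix D 4".

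D 4.1 opens with "If the subject does not meet PHL criteria the Investigator will" and contains one action: "Perform follow-up on subsequent laboratory results according to the guidance provided in the Clinical Study Protocol". D 4.2, directly below it, is for subjects who do meet the criteria. It asks for sponsor notification, monitoring, an aetiology work-up, three Liver CRF modules and SAE reporting if the case becomes serious. It also provides that "The Study Physician contacts the Investigator, to provide guidance, discuss and agree an approach" to follow-up. D 5 declares that it applies to every case meeting PHL criteria.

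**The concern.** The section exists only for subjects whose liver tests meet the criteria again, yet one of its branches points to the path for subjects whose tests do not. An investigator who follows the pointer does less for a repeat signal without a disease explanation than for one with a disease explanation and a significant change.

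What is at stake is handling and documentation of a rare but serious liver signal. The items affected are the work-up agreed with the Study Physician, the dedicated liver data capture, and certainty about the D 5 rule. Under that rule, when information is unavoidably delayed beyond three weeks, no alternative explanation is assumed and the case is reported as a Potential Hy's Law SAE.

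**Working it through.** No arithmetic in the plan bears on this, so the check is a comparison of the sections.

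**Entry conditions.** D 7 requires PHL criteria met now. D 4.1 requires PHL criteria not met. The two exclude each other, so no D 7 subject can properly enter D 4.1. D 4.2 is the path whose entry condition fits. Both sections are intact in the text, so the mismatch does not come from redaction or extraction.

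**What D 4.1 omits, and what survives elsewhere.**

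| D 4.2 item | Counterpart if only D 4.1 is followed |
|---|---|
| Notify the sponsor | Yes: D 3 already says "Notify the AstraZeneca representative" |
| Monitor liver biochemistry | Yes: Appendix F, hepatitis guidance |
| Investigate aetiology | Yes: Appendix F (any grade) and Section 8.4.5, but not as a work-up agreed with the Study Physician |
| Three Liver CRF modules | None |
| Report as SAE if serious | Yes: Section 8.4.1 |
| Study Physician contact and agreed approach | Not through D 4.1; discretionary in Appendix F; a contact also stands in D 5 |

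Of the five investigator actions, four have a counterpart: 5 − 4 = 1 without, namely the CRF modules. The Study Physician contact is a sixth item.

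**How far Appendix F reaches.** In the general hepatitis table, Grade 2 begins at bilirubin above 1.5 × ULN. A PHL bilirubin of at least 2 × ULN is therefore at least Grade 2 there, with liver tests checked, for example, every 1 to 2 days. This does not carry over to hepatocellular carcinoma. That table grades isolated transaminases only and handles bilirubin through a dosing rule, although liver monitoring at any grade still applies.

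**D 5 against D 7.** D 5 covers all PHL cases. D 7 says that whether a repeat case needs follow-up, review and assessment depends on the earlier cause, and it waives action for one group that does meet the criteria. So D 7 overrides D 5 for at least some repeats. The text does not state which section governs in the No branch.

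**Who can get there.** Two on-treatment PHL episodes are needed. Section 8.4.5 permanently stops drug when transaminases of at least 3 × ULN and bilirubin of at least 2 × ULN occur concurrently. It exempts events clearly not attributed to the drug from treatment modification. Two routes mainly remain:

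1. An earlier episode clearly due to a non-drug cause that D 7 does not count as the disease under study.
2. Elevations that were not concurrent, since D 2 sets no time frame between the two rises.

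The study plans at most 12 evaluable subjects.

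**Neighbouring references.** D 6 sends a significant change to Appendix B 5, which concerns important medical events; D 5 is the section that fits. D 1 cites Section 8.4.4 for managing liver abnormalities, but 8.4.4 is medication error and toxicity management is in 8.4.5.

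**The case against.** The best defence is that the pointer defeats itself. A reader sent to D 4.1 finds that it does not apply and sees D 4.2 directly below. D 4.1 itself refers back to the protocol, and Sections 8.2.1 and 8.3.9 return such cases to Appendix D. D 5 covers all PHL cases, and D 1 separately has the investigator and sponsor review cases meeting the criteria. In both D 4.2 and D 5 the Study Physician initiates the contact, and D 3 notification still reaches the sponsor. Section 8 also requires immediate safety concerns to be discussed with the sponsor at once.

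Most of this stands. A reader might infer that a No-branch case escapes the D 5 review, the default SAE rule and all Study Physician contact. The documents do not support that; they support only ambiguity. A reader might also infer that this branch holds the cases most likely to be drug-induced. That is not supported either: a first concurrent episode attributed to the drug ends treatment under 8.4.5, and D 5 makes it an SAE.

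Nor is the Yes branch wrong for citing D 4 as a whole, because a subject meeting PHL criteria falls under D 4.2.

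What the defence does not remove is the contradiction. The instruction as written cannot be followed, and D 7's own wording about the earlier cause prevents D 5's scope from settling the matter.

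**Conclusion.** The D 7 No branch is wrong as written and contradicts D 4.2 and the stated scope of D 5. On a literal reading it drops the D 4.2 work-up agreed with the Study Physician and the three Liver CRF modules. Whether the D 5 three-week review and its default SAE rule apply becomes ambiguous.

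Severity is minor. Very few subjects, possibly none, would reach this branch. The conclusion on rarity assumes that the 8.4.5 stopping rule is applied as written. DLTs are defined in Section 6.6.2 independently of Appendix D, so no DLT count changes, and no endpoint or analysis does either. It still deserves correction because it is an operative safety instruction, not background text.

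**What to change.** In D 7, change the destination of the No branch to D 4.2 followed by D 5. In the same edit, change Appendix B 5 in D 6 to Appendix D 5, and Section 8.4.4 in D 1 to Section 8.4.5. Naming D 4.2 in the Yes branch with significant change is optional and would only add clarity.

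The cost is three cross-reference corrections, or four with the optional one. No assessment is added beyond those D 4.2 and D 5 already require for PHL cases.
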